7.5. Replacement of Subjects

Subjects who are withdrawn for reasons other than AEs may be replaced at the discretion of the Sponsor.

7.6. Temporary Study Halt for Safety Review

The study will be temporarily halted, pending review of available data, if any of the following occur:

- If ≥ 2 subjects experience the same Grade 3 AE event or laboratory abnormality within 28 days after study drug administration, considered attributable to CD388 or cannot be attributed to another cause
(Investigator to consider the potential of IM injections to cause significant transient increases of creatine kinase [CK], when evaluating the potential relatedness of this laboratory abnormality to the investigational drug. A transient CK increase after IM injection is to be considered “not related” to the study drug.)
- If ≥ 1 subject experiences a Grade 4 AE or laboratory abnormality within 28 days after study drug administration, considered attributable to CD388 or cannot be attributed to another cause

If it is considered appropriate to restart the study following an internal safety review, a substantial amendment will be submitted to the Food and Drug Administration (FDA) and Institutional Review Board (IRB). The study will not restart until the amendment has been approved by the FDA and IRB.

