- Subject lost to follow-up, or follow-up is not possible
- The Investigator considers that it is in the subject's best interest not to continue participation in the study

Subject Stopping Rules

Additionally, subjects in Cohorts 2A, 2B, 3A, and 3B will be followed through Outpatient Visit 4 (OV4) of the first dosing period, and will not receive the second single dose:

- If the subject develops anaphylaxis or a related Grade 3 or Grade 4 AE
- If the subject has a persistent (i.e., >5 days with no response to treatment) Grade ≥ 2 rash considered related to the investigational drug by the Principal Investigator ([Appendix 4](#))
- If the Investigator believes that it is in the best interest of the subject to not receive a second dose.
- If the subject no longer meets all eligibility criteria prior to the second single dose
- If the subject becomes pregnant prior to the second single dose

If a subject is removed from the study for any reason, the subject will be followed for resolution of any ongoing AE(s).

Temporary Study Halt for Safety Review

The study will be temporarily halted, pending review of available data, if any of the following occur:

- If ≥ 2 subjects experience the same Grade 3 AE event or laboratory abnormality within 28 days after study drug administration, considered attributable to CD388 or cannot be attributed to another cause (Investigator to consider the potential of IM injections to cause significant transient increases of creatine kinase [CK], when evaluating the potential relatedness of this laboratory abnormality to the investigational drug. A transient CK increase after IM injection is to be considered "not related" to the study drug.)
- If ≥ 1 subject experiences a Grade 4 AE or laboratory abnormality within 28 days after study drug administration, considered attributable to CD388 or cannot be attributed to another cause

If it is considered appropriate to restart the study following an internal safety review, a substantial amendment will be submitted to the Food and Drug Administration (FDA) and Institutional Review Board (IRB). The study will not restart until the amendment has been approved by the FDA and IRB.

Statistical Methods

Safety, PK, and pharmacodynamics will be summarized using descriptive statistics. There will be no formal hypothesis testing. Analysis populations are:

- Safety Population: all subjects who receive any amount of study drug

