- e. Mean AUC_{0-3month} values (males and females combined) calculated over 3 months: rat by summing AUC from 3 doses and monkey by summing AUC from 2 doses, to cover a 3-month exposure period.
- f. Predicted human plasma PK for 50 mg starting dose (or 0.833 mg/kg based on a 60 kg person): AUC_{0-∞} = 3855 µg·h/mL. C_{max} = 14.4 µg/mL (calculated from 5 mg/kg IV human PK as reported/projected in NC-CD388-05). Note: These exposures were predicted for IV administration and would represent the highest values expected as bioavailability from IM or SQ administration is anticipated to be approximately 70% of IV based on animal PK studies, potentially lowering the exposures in human from IM or SQ dosing.

Safety results from this trial have indicated no significant safety findings following single IM or SQ administration of 50, 150 mg, and 450 mg CD388. Regular assessment of blinded safety/tolerability data from 66 healthy subjects who received a dose of 50 mg, 150 mg, or 450 mg of IM or SQ CD388 or placebo has not identified any concerning safety observations to date.

In summary, excellent safety margins were achieved with CD388 in 3-month toxicity studies relative to the proposed FIH human dose conservatively scaled to BSA and to the predicted FIH plasma exposure. Although no adverse findings were identified, transient minor changes in clinical pathology parameters were observed in the absence of other changes, including no changes in cytokines and microscopic findings, and no CD388-related effects on kidney or the reticuloendothelial system. The outcome of the CD388 nonclinical safety program supports the proposed clinical program. Results from this FIH study to date have shown no concerning safety findings after 50 mg, 150 mg, and 450 mg single-dose CD388 administrations.

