6. STUDY DESIGN

6.1. Description of the Study

This is a FIH, Phase 1, single-center, prospective, randomized, double-blind study of ascending single doses of CD388 Injection administered IM or SQ to healthy adult subjects followed by another single dose of CD388 Injection administered by the same route 3 months or 5 effective half-lives, whichever is longer, after the first dose in the middle and high dose groups (dosing may be adjusted for tolerability). The goals are to assess safety, tolerability, immunogenicity (anti-drug antibodies [ADA]), and PK of CD388.

Dose levels of CD388 to be assessed will follow an ascending single dose design with the starting dose based on findings from 3-month rat and monkey toxicology studies. Within each route (IM and SQ dose, route assignment is unblinded), subjects will be randomized to receive a single dose of CD388 Injection or saline placebo (treatment assignment is blinded) according to the design in [Table 5](#). It should be noted that each cohort will be divided into 2 groups identified as “sentinel” groups (randomized 1:1) and “main” groups (randomized 7:2):

- Low dose (50 mg) level: Cohort 1A (IM) and Cohort 1B (SQ) – each route n = 2 sentinel and n = 9 main
- Mid dose (150 mg) level: Cohort 2A (IM) and Cohort 2B (SQ) – each route n = 2 sentinel and n = 9 main
- High dose (450 mg) level: Cohort 3A (IM) and Cohort 3B (SQ) – each route n = 2 sentinel and n = 9 main
- Highest dose (900 mg) level: Cohort 4B (SQ) – n = 2 sentinel and n = 9 main

For each route, the sentinel or first group of 2 subjects (1 CD388: 1 placebo) at a dose level will be administered blinded study drug and closely monitored for safety for at least 1 week. The Principal Investigator (PI) and Sponsor will review blinded safety data after the initial sentinel group subjects at a dose level have completed dosing and followed for a minimum of 1 week. If no drug-related SAEs or drug-related Grade ≥ 3 AEs have occurred, the subjects in the corresponding main group may be dosed within 24 hours. The observation duration may be adjusted for the sentinel groups in Cohorts 2A, 2B, 3A, 3B, and 4B based on data from previous cohorts.

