Subjects in Cohorts 2A and 2B and Cohorts 3A and 3B will receive a second single dose of CD388 Injection or placebo after washout of 5 effective half-lives after the first dose if it is determined that the safety and tolerability of the first dose is acceptable upon review of the cumulative safety data. Immediately prior to the second single dose, within each dose and route, any dropouts in the sentinel groups will be randomly replaced with subjects from the main groups, retaining their original treatment assignment (i.e., subjects assigned to placebo will remain placebo, and subjects assigned to CD388 will remain CD388; this may require unblinded personnel to oversee).

The PI and Sponsor will review blinded safety data after the initial sentinel group subjects at a dose level have completed dosing and followed for the minimum observation period as determined during the first single dose. If no drug-related SAEs or drug-related Grade ≥ 3 AEs have occurred, the subjects in the corresponding main group may be dosed within 24 hours.

The dose escalation scheme is presented in [Section 1.2](#).

The Schedule of Events is presented in [Table 1](#) (first single dose, Cohorts 1A, 1B, 2A, 2B, 3A, 3B), [Table 2](#) (second single dose, Cohorts 2A, 2B, 3A, and 3B), and [Table 3](#) (single dose, Cohort 4B). All subjects will be admitted to the clinical research unit (CRU) for observation and safety assessments from Day -1 (check-in) to Day 30. Subjects will be monitored for AEs (including reactogenicity/injection site reactions and hypersensitivity reactions) and SAEs as indicated below:

Cohort	AE/SAE monitoring period from signing of ICF:
1A, 1B	Through 4 months after the dose of study drug
2A, 2B, 3A, 3B, 4B	Through 205 days after the last dose of study drug (Day 206 ±10 days)

Abbreviation: ICF = informed consent form.

Safety will also be assessed by physical examinations, ECGs, vital signs measurements, and laboratory evaluations (hematology, coagulation, serum chemistry, and urinalysis) at various time points during and after the CRU stay. Concomitant medication use will be recorded throughout the study.

Continuous 12-lead digital ECG recording will be performed using a 12-lead Holter ECG monitor as indicated below:

Cohort	Holter Monitoring Period
1A, 1B	1 hour before administration of study drug until 48 hours after dosing
2A, 2B, 3B	1 hour before first administration of study drug until 48 hours after dosing ^a

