6.2. Criteria for Evaluation

6.2.1. Safety and Tolerability of Study Drug

Safety and tolerability will be assessed by monitoring AEs (including reactogenicity/injection site reactions, hypersensitivity reactions, and adverse events of special interest [AESIs]), vital signs, 12-lead ECGs, Holter monitoring, clinical laboratory results (including hematology,

coagulation, serum chemistry, and urinalysis), and concomitant medication usage throughout the study.

See [Section 6.1](#) for details regarding dose level/cohort enrollment timing and assessment of safety and tolerability for dose escalation decision.

If a dose level is considered not safe or well tolerated, the study drug assignment for the subject(s) with the safety issue may be unblinded. The Sponsor may also independently decide to unblind the entire cohort for safety concerns or terminate enrollment for any reason.

If any subject develops a Grade ≥ 2 AE that is deemed related to the study drug, the mechanism of the AE may be assessed (i.e., cytokine level, complement activation, immunoglobulin G [IgG] subtypes, immunoglobulin E [IgE], T-cell/B-cell/monocyte and basophil activation as assessed by flow cytometry, ADA development, and immune complex formation) at Sponsor and Investigator discretion, and the study dose and route may be modified for the remainder of the study.

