11.4.4. Serious Adverse Event or Serious Suspected Adverse Reaction

An AE or suspected adverse reaction is considered “serious” if, in the view of either the Investigator or Sponsor, it results in any of the following outcomes:

- Death
- A life-threatening AE – see definition above
- Inpatient hospitalization or prolongation of existing hospitalization
- A persistent or significant incapacity or substantial disruption of the ability to conduct normal life functions
- A congenital anomaly/birth defect in the offspring of a subject who received study drug
- Is a suspected transmission of any infectious agent via a medicinal product
- Important medical events that may not result in death, be life-threatening, or require hospitalization may be considered serious when, based upon appropriate medical judgment, they may jeopardize the patient or subject and may require medical or surgical intervention to prevent one of the outcomes listed in this definition

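### The single-subject study halt names only Grade 4, so read literally an attributable death, which Table 9 grades as 5, need not trigger it

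*Protocol*

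**What the plan says.** Protocol Section 7.6 lists two events, either of which obliges the study to be halted:

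- at least two "subjects experience the same Grade 3 AE event or laboratory abnormality within 28 days after study drug administration";
- at least one "subject experiences a Grade 4 AE or laboratory abnormality within 28 days after study drug administration".

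Both carry the same attribution condition: the event is put down to CD388, or no other cause accounts for it. Restart then needs a substantial amendment approved by the FDA and the IRB. The synopsis gives the second trigger in the same words: "subject experiences a Grade 4 AE or laboratory abnormality within 28 days after study drug administration, considered attributable to CD388". Neither trigger mentions Grade 5, death or SAEs, and neither puts ≥ in front of the grade.

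Table 9 (Section 11.5.2), the general severity scale for AEs, has five grades. Grade 4 is potentially life-threatening; Grade 5 is death.

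The sentinel rule in Section 6.1 is worded differently: "If no drug-related SAEs or drug-related Grade ≥ 3 AEs have occurred, the subjects in the corresponding main group may be dosed". The same condition is repeated there for second doses. Under Section 11.4.4 an AE is serious if "it results in any of the following outcomes", and death heads the list that follows.

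**The concern.** A single-subject halt rule should catch the worst outcome on the scale it uses. This one stops one step short. As written, an attributable Grade 4 laboratory value within 28 days stops dosing across the study, yet an attributable death in the same window that was never recorded at Grade 4 matches neither trigger.

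Section 7.6 is the only provision that both halts the whole study automatically and ties restart to an approved amendment. If a death falls outside it, the response rests on narrower gates and on the sponsor's judgement. In a first-in-human study in healthy volunteers, that is the case in which a fixed rule matters most.

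**Working it through.** No sample-size or error-rate figure is involved, so the check sets the texts side by side.

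**Step 1. Map each Table 9 grade to the Section 7.6 triggers**, for an attributable AE within 28 days:

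| Grade | Halt required by the literal text? |
|---|---|
| 1–2 | No |
| 3 | Yes, if at least 2 subjects have the same event |
| 4 | Yes, at 1 subject |
| 5 (death) | No, unless the event was also recorded at Grade 4, or counts towards the same Grade 3 event in at least 2 subjects |

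**Step 2. Is Grade 5 really distinct in this study?** Yes. SAP Table 6 lists Death as a maximum-severity category apart from Life-threatening, and SAP Section 8.1 counts each preferred term at its highest severity. That governs tabulation rather than halting, but it shows that the two grades are kept apart.

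**Step 3. Does the protocol write 'or higher' elsewhere?** Yes: Grade ≥3 in Section 6.1, Grade ≥2 in Section 6.2.1, graded laboratory exclusions in Section 7.2, and Grade ≥2 rash in Section 7.4.1. This is supporting evidence only. The Grade 3 trigger in Section 7.6 also lacks ≥, and two scales (Table 7 and the fever scale in Appendix 2) stop at Grade 4.

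**Step 4. Would another provision do the same job?**

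- *Sentinel gate (Section 6.1).* Mandatory, and it covers a drug-related death because death is an SAE. It blocks only the corresponding main group. It does not reach a death in a main-group subject and does not stop other cohorts.
- *Escalation review (Section 6.1).* It controls the next dose level. Cohort 4B, at 900 mg, is the highest level, so nothing follows it.
- *Cumulative review before second doses (Section 6.1).* It applies to Cohorts 2A, 2B, 3A and 3B. Cohort 4B gets a single dose.
- *Section 6.2.1.* "The Sponsor may also independently decide to unblind the entire cohort for safety concerns or terminate enrollment for any reason". This is discretionary, as is termination under Section 7.7.
- *SAE and SUSAR reporting (Section 11.3.1) and urgent safety measures (Sections 11.3.2 and 11.4.8).* None is an automatic halt.

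**Step 5. Which doses could still be outstanding under this version?** Section 4.3 refers to "Regular assessment of blinded safety/tolerability data from 66 healthy subjects who received a dose of 50 mg, 150 mg, or 450 mg", out of 77 planned.

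- First doses left: 77 − 66 = 11. This matches Cohort 4B: CD388 1 + 7 = 8, placebo 1 + 2 = 3, total 11.
- Second doses: "Subjects in Cohorts 2A and 2B and Cohorts 3A and 3B will receive a second single dose of CD388 Injection or placebo". The maximum is 4 × 11 = 44 (CD388 4 × 8 = 32; placebo 4 × 3 = 12). The number already given is not stated, so between 0 and 44 remain (0 to 32 CD388).

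These counts bound what was outstanding; they do not measure impact. The dose that precedes a death cannot be prevented, a drug-related sentinel death is already gated, and second doses also need an acceptable cumulative review.

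**The case against.** The strongest reply is that the trigger is a floor. If a potentially life-threatening event stops the study, a fatal one does so all the more, and no sponsor would read it otherwise. The rule also turns on what a subject experiences, not on what is recorded. Most people dying of a drug effect would pass through a Grade 4 state and so meet the trigger. Subjects are inpatients under continuous medical supervision through Day 30 (Sections 4.2 and 6.1), which spans the 28-day window and makes an unwitnessed death unlikely. The missing ≥ looks like the section's style, not a decision to exempt deaths. The dose counts prove nothing about harm.

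Most of this stands, and it is why the point is minor. The exposed case is rare, and nothing suggests that the sponsor meant to leave deaths out. What does not follow is that the text is adequate. A sudden death, or one graded only by its fatal outcome, still matches neither trigger, and a mandatory safety rule should not need inference at its most extreme case. The other safeguards are real but narrower or discretionary.

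**Conclusion.** The concern holds as a minor wording fault in two places: Section 7.6 and the synopsis. It rests on a literal reading of the trigger, on Table 9 being the scale applied to a fatal AE, and on the death having no recorded Grade 4 phase. Within those limits, nothing in the protocol or SAP supplies an equivalent automatic halt. The practical risk is low, because the sponsor would very likely stop dosing regardless. No number of protected doses is claimed, and no estimand, sample size or analysis changes.

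**What to change.** In Section 7.6 and in the synopsis, reword the event in the second trigger as: *Grade ≥4 AE (including death) or Grade 4 laboratory abnormality*. Keep the one-subject threshold, the 28-day window and the attribution condition. Leave the Grade 3 trigger and the sentinel gate as they are. The cost is one phrase in two places, with no change to procedures, data collection or analysis.

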7.7. Study Termination by Sponsor and Termination Criteria

The Sponsor reserves the right to terminate an investigational site or this clinical study at any time. Reasons for termination may include, but are not limited to, the following:

- The incidence or severity of AEs indicate a potential health hazard to subjects.
- Serious or persistent noncompliance by the Investigator with the protocol, clinical research agreement, or applicable regulatory guidelines in conducting the study.
- Institutional Review Board (IRB)/Independent Ethics Committee (IEC) decision to terminate or suspend approval for the investigation or the Investigator.
- Investigator request to withdraw from participation.
- Subject enrollment is unsatisfactory.

8. STUDY DRUG

8.1. CD388 Injection

CD388 Injection is a clear to lightly opalescent liquid essentially free of particulate matter containing the active pharmaceutical ingredient, CD388. CD388 Injection is supplied as a frozen sterile solution in single-use vials. Refer to the Pharmacy Manual for details.

CD388 Injection is administered by either IM or SQ injection at the dose described in [Table 5](#), depending upon the subject's randomization assignment. Dose levels to be assessed will follow an ascending single-dose regimen with the starting dose based on findings from 3-month rat and monkey toxicology studies.

8.1.1. Directions for Use

CD388 Injection should be thawed at room temperature over 30 minutes (not to exceed 24 hours) prior to drawing the dose from the vial into the syringe.

After CD388 Injection is drawn from the vial into the syringe, it must be administered within 4 hours.

8.1.2. Drug Storage

Vials of CD388 Injection should be stored frozen at -20°C.

8.1.3. Dose Adjustment

Dosage adjustments of CD388 Injection in individual subjects are not allowed in this study.

8.2. Placebo Injection

Normal saline will be administered IM or SQ as the placebo control.

8.3. Compliance

Treatment compliance for CD388 Injection/placebo will be documented in the eCRF by recording the date, administration time, and the volume of the dose of study drug administered.

8.4. Breaking the Blind

The study is a double-blind design. The Sponsor, Investigator, study site personnel, and subjects will not make any effort to determine which blinded study drug (CD388 Injection or placebo) is administered. Unblinded pharmacy personnel will be responsible for preparing syringes such that the double-blind is maintained.

Only in the case of an emergency, when knowledge of the study drug is essential for the clinical management or welfare of a specific subject, may the Investigator unblind a subject's study drug assignment.

As soon as possible and without revealing the subject's study drug assignment (unless important to the safety of subjects remaining in the study), the Investigator must notify the Sponsor if the

blind is broken for any reason. The Investigator will record in source documentation the date and reason for revealing the blinded study drug assignment for that subject.

As PK samples from subjects assigned to placebo treatment will not be analyzed for determination of CD388 concentrations, the bioanalytical laboratory will receive the randomization list to allow for correct selection of the samples. Unblinding of the randomized treatment assignment will be performed at the bioanalytical laboratory. Specific procedures will be in place to ensure that randomized treatment assignment will not be revealed to anyone involved in the execution of the study.

The Sponsor may conduct an interim analysis of selected safety and efficacy study data. Study team members involved in day-to-day trial related activities will not have access to interim analysis data which might unblind them at the subject level. Unblinding at treatment/group level is permitted as needed to enable the analysis. After the database is locked and the Statistical Analysis Plan (SAP) is final, the study blind codes will be broken.

8.5. Previous and Concomitant Medications and Substances

All medications administered within 30 days prior to study drug administration and throughout the study will be documented and recorded in the eCRF.

Subjects must refrain from over-the-counter (OTC) and nutritional supplements within 7 days and prescription medications within 14 days or <5 half-lives before first study drug administration, and until after the final study visit (except for hormonal contraceptives, acetaminophen, or ibuprofen). The Investigator should consult the Sponsor's Medical Monitor for guidance regarding other medication or vaccine usage during the study.

